#### 8.5.2. Secondary Analyses

The proportion of subjects with HIV-1 RNA < 50 copies/mL at Week 48 as defined by the US FDA-defined snapshot algorithm will also be summarized. The 95% CIs will be constructed in the same manner as described for the primary efficacy endpoint. However, non-inferiority will be assessed using a margin of 10%. It will be concluded that B/F/TAF FDC is noninferior to DTG+F/TAF if the lower bound of the 2-sided 95% CI of the difference between treatment groups (B/F/TAF group – DTG+F/TAF group) in the response rate is greater than -10%.

The change from baseline in CD4+ cell count at Week 48 will be summarized by treatment using descriptive statistics. The differences and the associated 95% CIs will be constructed using an Analysis of Variance (ANOVA) model, including treatment (B/F/TAF group vs. DTG+F/TAF group), prior NRTI use (F/TAF vs. F/TDF) and history of NRTI resistance as fixed effects in the model.

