# Study Day 1 for the all B/F/TAF analysis is defined as

- For subjects who actually received B/F/TAF in the randomized phase of this study (ie, B/F/TAF group), **Study Day 1** for the all B/F/TAF analysis is defined as the day when the first dose of B/F/TAF in the randomized phase was taken, as recorded on the Study Drug Administration eCRF form.
- For subjects who actually received DTG + F/TAF in the randomized phase of this study and then receive at least 1 dose of B/F/TAF in the extension phase (ie, DTG + F/TAF to B/F/TAF group), **Study Day 1** for the all B/F/TAF analysis is defined as the day when the first dose of B/F/TAF in the extension phase was taken (ie, OL B/F/TAF), as recorded on the Study Drug Administration eCRF form.

Last Dose Date for the All B/F/TAF Analysis is the latest of B/F/TAF (including both randomized phase and open label phase) end dates recorded on the Study Drug Administration eCRF form.

If the last dose date for the all B/F/TAF analysis is missing (eg, only year of last dose date is known or completely missing due to lost to follow-up), the latest of the B/F/TAF (including both randomized phase and open label phase) start dates and end dates, the latest clinical and laboratory visit dates, excluding the 30-day follow-up visit date, will be used to impute the last dose date.

**Study Days** are calculated relative to Study Day 1 for the randomized phase analysis. For events that occurred on or after the Study Day 1 date, study days are calculated as (visit date minus Study Day 1 plus 1). For events that occurred prior to Study Day 1 for either analysis, study days are calculated as (visit date minus Study Day 1).

**Last Study Date** is the latest of the study drug (including DTG + F/TAF, and B/F/TAF in both randomized phase and open label phase) start dates and end dates, the clinic visit dates, and the laboratory visit dates, including the 30-day follow-up visit date.

**Baseline Value** is defined as the last nonmissing value obtained on or prior to Study Day 1 for the randomized phase analysis or the all B/F/TAF analysis, as appropriate. Subjects who actually received DTG + F/TAF in the randomized phase and received at least 1 dose of B/F/TAF in extension phase will have a baseline for Randomized Phase Analysis and a new baseline value for the all B/F/TAF analysis.

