#### 6.1.2. Secondary Efficacy Endpoints

6.1.2.1. Definition of the Secondary Efficacy Endpoints

The secondary efficacy endpoints include:

- The proportion of subjects with HIV-1 RNA < 50 copies/mL at Week 48 as determined by the US FDA-defined snapshot algorithm
- The change from baseline in CD4+ cell count at Week 48

The analyses for the secondary efficacy endpoints will be conducted using the FAS and the Week 48 PP analysis set, respectively.

- 6.1.2.2. Analysis of the Secondary Efficacy Endpoints
- 6.1.2.2.1. Analysis of the Proportion of Subjects with HIV-1 RNA < 50 copies/mL as Determined by US FDA-defined Snapshot Algorithm

The proportion of subjects with HIV-1 RNA < 50 copies/mL at Week 48 will also be analyzed by the US FDA-defined snapshot algorithm based on the FAS and Week 48 PP analysis set, respectively.

Proportion of subjects with HIV-1 RNA < 50 copies/mL at Week 48 as determined by US FDA-defined snapshot algorithm will be analyzed similarly to the primary efficacy endpoint. However, the noninferiority margin used for the proportion of subjects with HIV-1 RNA < 50 copies/mL will be 10%.

Similarly to the primary efficacy endpoint, noninferiority will be assessed using the conventional CI approach. The point estimate of treatment difference (B/F/TAF group – DTG+F/TAF group) in the percentage of subjects with HIV-1 RNA < 50 copies/mL and the associated 2-sided 95.001% CI will be constructed based on an unconditional exact method using 2 inverted 1-sided tests.

It will be concluded that B/F/TAF is noninferior to DTG+F/TAF if the lower bound of the 2-sided 95.001% CI of the difference between treatment groups (B/F/TAF group – DTG+F/TAF group) in the percentage of subjects with HIV-1 RNA < 50 copies/mL is greater than –10%.

The above analysis will be performed using both the FAS and the Week 48 PP analysis set.

In addition, the following analyses will be performed using the FAS to evaluate the interaction between region and treatment to assess homogeneity of treatment effect across different regions.

A region is defined as multiple sites combined based on geographical locations (see Appendix 2 for region definition).

For each region, the difference in the proportion of subjects with HIV-1 RNA < 50 copies/mL between treatment groups and its 95% CI will be calculated based on an unconditional exact method using 2 inverted 1-sided tests.

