## 6.1.2.2.3 Analysis of CD4+ Cell Count

All CD4+ cell count will be summarized by visit using observed, on-treatment data (ie, data collected up to 1 day after permanent discontinuation of blinded study drug) for subjects in the FAS for randomized phase analysis and for subjects in all B/F/TAF Analysis Set for all B/F/TAF analysis.

The changes from baseline in CD4+ cell count at Week 48 will be summarized by treatment group using descriptive statistics for randomized phase analysis. The differences in changes from baseline in CD4+ cell count between the 2 treatment groups and the associated 95% CI will be constructed using analysis of variance (ANOVA) models, including treatment group as a fixed effect in the model. The change from baseline in CD4+ cell count will also be summarized at visits other than Week 48 by treatment group for the FAS for randomized phase analysis.

The change from baseline in CD4+ cell counts will also be analyzed based on the Week 48 PP analysis set for randomized phase analysis.

[figure not shown]
The mean and 95% CI of change from baseline in CD4+ cell count over time will be plotted for the FAS for randomized phase analysis.

In addition, the change from baseline in CD4+ cell counts with missing values imputed using the last observation carried forward (LOCF) method will be summarized at each visit (up to week 48 visit) based on the FAS for randomized phase analysis. The algorithm for LOCF is as follows:

- If a value is missing in an analysis visit window, the missing value will be replaced with the
  last on-treatment value (ie, data collected up to 1 day after permanent discontinuation of
  study drug) observed before the analysis visit window that has the missing value.
- Baseline values will be carried forward to impute the postbaseline value at a specific visit, if there is no non-missing postbaseline observation collected prior to that visit.

The changes from baseline in CD4+ cell count will be summarized by treatment group and scheduled visits using descriptive for all B/F/TAF analysis.

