## 6.3. Changes From Protocol-Specified Efficacy Analyses

No change from the protocol-specified efficacy analysis is planned.

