estimate 'Group 1' trtgrpn 1 -1 trtgrpn*agegrp 1 0 -1 0/exp;
estimate 'Group 2' trtgrpn 1 -1 trtgrpn*agegrp 0 1 0 -1/exp;
run;
```

Note: trtgrpn is the numeric treatment group variable, response is the response outcome variable (1 vs 0 ('<50' vs'>=50')), agegrp is the subgroup variable for age (1:<50 vs 2: >=50).

(P-value for the homogeneity test was based on the Wald test of the interaction between treatment and subgroup. Odds ratio is from L'Beta estimate, its 95%CI is from L'Beta confidence limits for each subgroup.)

i) ANOVA model for continuous efficacy variable (eg, CD4): The differences in changes from baseline in CD4 cell count between treatment groups and the associated 95% CI will be constructed using an ANOVA, including treatment as fixed effect in the model.

```
proc glm data=adeff;
     class trtgrp;
     model CD4=trtgrp;
     lsmeans trtgrp /alpha=0.05 cl pdiff;
run;
```

j) Listing for US FDA-defined snapshot outcome:

In addition to flagging the values of HIV-1 RNA < 50 or  $\ge 50$  copies/mL for virologic outcomes, flag the last available HIV-1 RNA value while on treatment for the following categories:

- i) HIV-1 RNA >= 50 copies/mL Discontinued Study Drug Due to AE or Death and Last Available HIV-1 RNA >= 50 copies/mL
- ii) HIV-1 RNA >= 50 copies/mL Discontinued Study Drug Due to Other reason\* and Last Available HIV-1 RNA >= 50 copies/mL
- iii) No virologic Data Discontinued Study Drug Due to AE or Death and Last Available HIV-1 RNA < 50 copies/mL
- iv) No virologic Data Discontinued Study Drug Due to Other reason\* and Last Available HIV-1 RNA < 50 copies/mL
- Note: \* Other reasons include subjects who discontinued study drug due to investigator's discretion, subject decision, lost to follow-up, noncompliance with study drug, protocol violation, pregnancy, and study terminated by sponsor.
- 15) Clarification of the following LOCF algorithms:
  - Baseline values will be carried forward.
  - For CD4:

If a value is missing in an analysis visit window, replace the missing value with the last on-treatment value observed before the analysis visit window that has the missing value.

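### The Week 48 CD4+ comparison leaves baseline CD4+ out of the model: a valid analysis, but less precise than an ANCOVA on data already in hand

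*SAP*

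**What the plan says.** - **Endpoint.** SAP 6.1.2.1 lists "The change from baseline in CD4+ cell count at Week 48" as one of two secondary efficacy endpoints; protocol 8.1.3 agrees.
- **Protocol model.** Protocol 8.5.2 states: "The differences and the associated 95% CIs will be constructed using an Analysis of Variance (ANOVA) model, including treatment", followed by "prior NRTI use (F/TAF vs. F/TDF) and history of NRTI resistance as fixed effects in the model". The synopsis gives the same three terms.
- **SAP model.** SAP 6.1.2.2.3 has the difference and CI "constructed using analysis of variance (ANOVA) models, including treatment group as a fixed effect in the model". Appendix 8 item 14i repeats this ("including treatment as fixed effect in the model") and its code reads "model CD4=trtgrp".
- **Other CD4+ analyses.** SAP 6.1.2.2.3 repeats the analysis on the Week 48 PP set without naming another model. The LOCF version is a descriptive summary. No planned CD4+ comparison therefore adjusts for baseline.
- **Availability of baseline.** The study procedures table schedules CD4+ at Screening and Day 1. SAP 3.8.1 defines baseline as the "last nonmissing value obtained on or prior to Study Day 1 for the randomized phase analysis". SAP 5.2 tabulates baseline CD4+ and compares the arms on it.
- **Declared changes.** SAP 6.3 states: "No change from the protocol-specified efficacy analysis is planned".

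**The concern.** A change-score ANOVA fixes the slope of Week 48 CD4+ on baseline CD4+ at 1. When the true slope is below 1, two things follow. The residual variance is larger than it needs to be, so the interval for the treatment difference is wider than the data require. And a chance difference between arms at baseline is only partly removed by the subtraction, with the remainder entering the estimate in the opposite direction.

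The plan would display a baseline imbalance through SAP 5.2 but contains no CD4+ analysis that accounts for one. Restoring the protocol's two stratification factors would not change this, since neither document has baseline CD4+ in the model. What is at stake is the precision and stability of the estimate for a named secondary endpoint.

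**Working it through.** **The plan's own figures.** The documents give no sample size, SD, effect size or power for CD4+. Their calculations concern the primary endpoint and reproduce: 258 per arm by normal approximation against 260 planned, 90.3% power at 260 per arm, and 85.1% by the exact method at 283/282 against the 85% in SAP 1.4. Nothing below depends on them.

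**Inputs.**
- N = 565 (SAP 1.4). The split by arm is not stated; 283/282 is assumed.
- ρ, the correlation of baseline with Week 48 CD4+, is not in the documents. Assumed range: 0.6 to 0.9.
- Equal SD *s* at the two times is assumed.

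**Variances.**
- Change-score ANOVA: s² + s² − 2ρs² = 2s²(1−ρ).
- ANCOVA: s²(1−ρ²).
- Ratio ANCOVA/ANOVA: (1−ρ²) / [2(1−ρ)] = (1+ρ)/2.

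**Imbalance.** For a baseline difference D between arms, the change-score estimate shifts by (ρ−1)D = −(1−ρ)D. The ANCOVA estimate shifts by about zero.

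| ρ | Variance ratio (1+ρ)/2 | CI narrower by 1−√ratio | Equivalent extra subjects, 1/ratio − 1 | Share of D retained, 1−ρ |
|---|---|---|---|---|
| 0.6 | 0.80 | 10.6% | 25.0% | 0.40 |
| 0.7 | 0.85 | 7.8% | 17.6% | 0.30 |
| 0.8 | 0.90 | 5.1% | 11.1% | 0.20 |
| 0.9 | 0.95 | 2.5% | 5.3% | 0.10 |

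A simulation of 3,000 trials at 283/282 gave variance ratios of 0.80, 0.92 and 0.95 at ρ = 0.6, 0.8 and 0.9. The change-score estimate moved with D at slopes of −0.40, −0.19 and −0.10; the ANCOVA slopes were all within 0.01 of zero. This agrees with the algebra apart from simulation noise.

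**Unequal SDs.** With SDs s₀ and s₁, the ANOVA variance minus the ANCOVA variance is s₀² + s₁² − 2ρs₀s₁ − s₁²(1−ρ²) = (s₀ − ρs₁)². This is never negative, and is zero only when the slope ρs₁/s₀ equals 1. In large samples, then, the covariate does not cost precision.

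**Scale in cells/µL.** Take s = 250 as an assumption, with √(1/283 + 1/282) = 0.0841. The ANOVA half-width is 1.96 × 250 × √(2(1−ρ)) × 0.0841. A 1-SE baseline imbalance is 250 × 0.0841 = 21.0.

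| ρ | Half-width, ANOVA | Half-width, ANCOVA | Size of shift from a 1-SE imbalance, (1−ρ) × 21.0 |
|---|---|---|---|
| 0.6 | 36.9 | 33.0 | 8.4 |
| 0.7 | 31.9 | 29.4 | 6.3 |
| 0.8 | 26.1 | 24.7 | 4.2 |
| 0.9 | 18.4 | 18.0 | 2.1 |

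The only CD4+ change SDs in the documents come from the Phase 2 study in treatment-naive subjects (protocol 1.2.3.3). Using its 221.7 for scale only, the half-width is 1.96 × 221.7 × 0.0841 = 36.6, falling to 32.7, 33.7, 34.7 or 35.6 at ρ = 0.6, 0.7, 0.8 or 0.9. SAP 6.1.2.2.3 uses observed on-treatment values, so fewer than 565 subjects may contribute and absolute widths may be somewhat larger. The ratios do not depend on N.

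**The case against.** The strongest reply is that nothing turns on this endpoint. The CD4+ difference has no margin, success rule or power calculation, and SAP 3.5 adjusts alpha only for the two HIV-1 RNA endpoints. An interval a few percent narrower would not alter any stated decision. That stands.

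Second, the planned analysis is sound. A reader might infer from the missing covariate that the CD4+ estimate is biased or its interval invalid. The documents do not support that: under 1:1 randomization the change-score difference is unbiased, and chance imbalance is already part of its sampling variance. Subtracting baseline also removes most of any imbalance over the range of ρ considered. At s = 250 and ρ = 0.8, a 1-SE imbalance moves the estimate by 4.2 against a half-width of 26.1, and SAP 5.2 would make a sizeable imbalance visible.

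Third, the size of the gain is assumed. No ρ or CD4+ variance is given for virologically suppressed subjects, and at ρ = 0.9 the interval narrows by only 2.5%.

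Fourth, timing. SAP 2.2.1 reports that the Week 48 analysis has been conducted, while this SAP governs the final analysis (SAP 2.3). Replacing the model now would be a post hoc change. That rules out substitution but not a supportive analysis identified as such.

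What remains is that the covariate is already measured, loses no subject who has a change score, and in large samples cannot worsen precision.

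**Conclusion.** The point holds as one of efficiency. No planned CD4+ comparison uses baseline CD4+. Under equal SDs and ρ between 0.6 and 0.9, adding it would narrow the interval by about 11% to 2.5%, worth about 25% to 5% more subjects, and would remove the −(1−ρ) carry-over of chance baseline differences. The omission can be read directly from the text; its size rests on the assumed ρ and is modest at the upper end.

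A reader might also infer that the non-inferiority result is in doubt. It is not: the primary endpoint is a snapshot proportion analysed by an unconditional exact method that makes no use of CD4+.

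The SAP's omission of the protocol's two stratification factors, alongside its statement in 6.3 that nothing changed, is a separate inconsistency in the same model. The supportive analysis should not repeat it.

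**What to change.** In SAP 6.1.2.2.3 and Appendix 8 item 14i, add an ANCOVA of Week 48 CD4+ change with four terms: treatment, baseline CD4+ as a continuous covariate, prior NRTI use, and NRTI resistance history. Report the adjusted LS-mean difference and 95% CI for the FAS and the Week 48 PP set.

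Present it beside the planned ANOVA as a labelled supportive analysis, and record it in SAP 6.3 with the reason and the fact that it was added after the Week 48 analysis. Do not amend protocol 8.5.2 retrospectively.

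State in the code that the response is change, since item 14i names it only as CD4. With baseline in the model, the treatment coefficient is the same for change or for the Week 48 value.

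The cost is one extra model and its output for two analysis sets, plus a line in SAP 6.3. No new data are needed.

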## 6.2. Efficacy Analysis for All B/F/TAF Analysis

## 6.2.1. Definition of the Efficacy Endpoint

The efficacy endpoints for all B/F/TAF analysis include:

- The proportion of subjects with HIV-1 RNA < 50 copies/mL by M = E approach
- The change from baseline in CD4+ Cell Count and CD4 percentage (%) by visit

The analyses for the efficacy endpoints above will be conducted using the All B/F/TAF Analysis Set.

#### 6.2.2. Analysis of the Efficacy Endpoints for All B/F/TAF Analysis

6.2.2.1. Analysis of the Proportion of Subjects with HIV-1 RNA < 50 copies/mL by Missing = Excluded Approach

The proportion of subjects with HIV-1 RNA < 50 copies/mL will be analyzed using M = E for imputing missing HIV-1 RNA values using the All B/F/TAF Analysis Set for the all B/F/TAF analysis.

• Missing = Excluded (M = E)

In this approach, all missing data will be excluded in the computation of the percentages (ie, missing data points will be excluded from both the numerator and denominator in the computation). The denominator for percentages at a visit is the number of subjects in the All B/F/TAF Analysis Set with non-missing HIV-1 RNA value at that visit.

For M = E analysis, the number and percentage of subjects with HIV-1 RNA in the following categories will be summarized:

- < 50 copies/mL
  - -- < 20 copies/mL
    - < 20 copies/mL Not Detectable

    - < 20 copies/mL Detectable
  - -20 to < 50 copies/mL
- 50 to < 200 copies/mL
- 200 to < 400 copies/mL
- 400 to < 1000 copies/mL
- $\geq 1000 \text{ copies/mL}$

The 95% CI for the proportion of subjects with HIV-1 RNA < 50 copies/mL for a treatment group will be constructed using the Clopper-Pearson exact method. No statistical comparisons will be made for the all B/F/TAF analysis.

## 6.2.2.2. Analysis of CD4+ Cell Count and CD4%

The analysis of CD4 cell count will be based on on-treatment data (ie, up to 1 day after the last dose date of study drug) using the All B/F/TAF Analysis Set for the all B/F/TAF analysis.

The changes from baseline in CD4+ cell count at each visit will be summarized by treatment group using descriptive statistics. No statistical comparisons will be made for the all B/F/TAF analysis.

Similar analysis will be conducted for CD4% using the All B/F/TAF Analysis Set for the all B/F/TAF analysis.

In addition, the mean and 95% CI of change from baseline in CD4+ cell count over time will be plotted for the all B/F/TAF analysis.

## 6.3. Changes From Protocol-Specified Efficacy Analyses

No change from the protocol-specified efficacy analysis is planned.

#### 7. SAFETY ANALYSES

Safety data will be summarized by treatment group for the subjects in the Safety Analysis Set for the randomized phase analysis, and the subjects in the All B/F/TAF Analysis Set for the all B/F/TAF analysis, unless specified otherwise. All safety data from both phases of the study will be included in data listings.

For the randomized phase analysis, the terms "study drug start date (ie, the first dose date)", "study drug stop date (ie, the last dose date)", and "baseline" in the text below refer to the first dose date, the last dose date, and baseline defined for the randomized phase analysis; the term "study drug" in the text below refer to the randomized study drugs.

For the all B/F/TAF analysis, the terms "study drug start date (ie, the first dose date)", "study drug stop date (ie, the last dose date)", and "baseline" in the text below refer to the first dose date, the last dose date, and baseline defined for the all B/F/TAF analysis; the term "study drug" in the text below refer to B/F/TAF.

#### 7.1. Adverse Events and Deaths

## 7.1.1. Adverse Event Dictionary

Clinical and laboratory AEs will be coded using the current version of MedDRA. System organ class (SOC), high-level group term (HLGT), high-level term (HLT), preferred term (PT), and lowest-level term (LLT) will be provided in the AE dataset.

#### 7.1.2. Adverse Event Severity

Adverse events are graded by the investigator as Grade 1 (mild), Grade 2 (moderate), Grade 3 (severe) or Grade 4 (life threatening) according to toxicity criteria specified in the protocol. The severity grade of events for which the investigator did not record severity will be left as "missing" for data listings.

## 7.1.3. Relationship of Adverse Events to Study Drug

Related AEs are those for which the investigator selected "Related" on the AE eCRF to the question of "Related to Study Treatment." Events for which the investigator did not record relationship to study drug will be considered related to study drug for summary purposes. However, by-subject data listings will show the relationship as missing.

#### 7.1.4. Serious Adverse Events

Serious adverse events (SAEs) will be identified and captured as SAEs if AEs met the definitions of SAE specified in the study protocol. Serious adverse events captured and stored in the clinical database will be reconciled with the SAE database from the Global Patient Safety (GLPS) Department before data finalization.

## 7.1.5. Treatment-Emergent Adverse Events

## 7.1.5.1. Definition of Treatment-Emergent Adverse Events

Treatment-emergent adverse events (TEAEs) are defined as 1 or both of the following:

- Any AEs with an onset date on or after the study drug start date and no later than 30 days after permanent discontinuation of the study drug, or
- Any AEs leading to premature discontinuation of study drug.

More specifically, the AE onset date will be compared with the first and last randomized study drug dates for the randomized phase analysis. For the all B/F/TAF analysis, the AE onset date will be compared with the first and last study drug dates.

#### 7.1.5.2. Incomplete Dates

If the onset date of the AE is incomplete and the AE stop date is not prior to the first dosing date of study drug, then the month and year (or year alone if month is not recorded) of onset determine whether an AE is treatment emergent. The event is considered treatment emergent if both of the following 2 criteria are met:

- The month and year (or year) of the AE onset is the same as or after the month and year (or year) of the first dosing date of study drug, and
- The month and year (or year) of the AE onset is the same as or before the month and year (or year) of the date corresponding to 30 days after the date of the last dose of study drug

An AE with completely missing onset date and stop date or with the onset date missing and a stop date marked as ongoing or on or after the first dosing date of study drug, will be considered to be treatment emergent. In addition, an AE with the onset date missing and incomplete stop date with the same or later month and year (or year alone if month is not recorded) as the first dosing date of study drug will be considered treatment emergent.

